**Table 8: Corticosteroid Dose Tapering Sequence by Dose at Randomization (Visit B1)**

Sequence	Prednisone or Equivalent Dose (mg/day) at Randomization								
	25	20	17.5	15	12.5	10	7.5	5	2.5
Taper 1	20	17.5	15	12.5	10	7.5	5	2.5	0
Taper 2	17.5	15	12.5	10	7.5	5	2.5	0	
Taper 3	15	12.5	10	7.5	5	2.5	0		
Taper 4	12.5	10	7.5	5	2.5	0			
Taper 5	10	7.5	5	2.5	0				
Taper 6	7.5	5	2.5	0					
Taper 7	5	2.5	0						
Taper 8	2.5	0							
Taper 9	0								

### 6.7 Treatment After the End of the Study

At the end of the study, the investigator should encourage subjects to continue appropriate standard medical care for SLE and LN.

In addition, for subjects who continue to demonstrate clinical benefit, BMS may elect to continue to provide study treatment via an extension of the current study, a rollover study requiring approval by responsible health authority and ethics committee, or through another mechanism at the discretion of BMS.

BMS reserves the right to terminate access to BMS-supplied study treatment if any of the following occur:

- a. The study is terminated due to safety concerns or other reasons, including but not limited to lack of efficacy and/or failure to meet study objectives
- b. Development of BMS-986165 for the treatment of LN and/or the development of the compound is terminated for other reasons, including but not limited to lack of efficacy and/or failure to meet study objectives
- c. The subject can obtain medication from a government-sponsored or private health program; in all cases, BMS will follow local regulations

### 6.8 Preparation/Handling/Storage/Accountability

All IP (MMF and blinded study treatment) should be stored in a secure area according to local regulations. It is the responsibility of the investigator to ensure that IP is dispensed only to study subjects. The IP must be dispensed only from official study sites by authorized personnel according to local regulations.

The product storage manager should ensure that all study treatments are stored in accordance with the environmental conditions (temperature, light, or humidity) as determined by BMS. If concerns regarding the quality or appearance of the blinded IP arise, the study treatment should not be dispensed and the investigator should contact BMS immediately.

Study-supplied MMF should be stored according to the instructions on the packaging.

Study treatment not supplied by BMS will be stored in accordance with the package insert.

Investigational product documentation (whether the IP is supplied by BMS or not) must be maintained and must include all processes required to ensure drug is accurately administered. This includes documentation of drug storage, administration and, as applicable, storage temperatures, reconstitution, and use of required processes (eg, required diluents, administration sets). Further guidance and information for final disposition of unused study treatment are provided in [APPENDIX 2](#).

### **6.8.1 Retained Samples for Bioavailability/Bioequivalence**

Not applicable

### **6.9 Treatment Compliance**

Compliance with MMF and blinded study treatment will be monitored using standard drug accountability procedures such as comparing the number of tablets returned to the number dispensed, according to the expected regimen and any reported missed doses. Subjects should be instructed to bring all unused MMF and blinded IP to each study visit. Drug accountability will be reviewed by the investigative site staff at each visit to confirm treatment compliance. Site staff will discuss any discrepancies and remind the subject of the importance of compliance with the assigned regimen. A real-time monitoring platform may be used.

Several times during the study, compliance with MMF therapy will be assessed by measuring the trough MPA concentration.

### **6.10 Previous and Concomitant Therapy**

All previous medications for SLE will be recorded.

All medications (including MMF obtained outside the study) taken within 4 weeks before the first dose of study-supplied MMF in Part A through the final study visit must be recorded on the concomitant medication electronic case report form (eCRF). The only exception is that corticosteroids must be recorded on the Corticosteroid Dose Log starting at Visit B1.

Corticosteroid dosage and tapering guidelines are discussed in [Section 6.6.1](#).

Changes in dosing of SLE medications in the 12 weeks before screening should be recorded, but with regard to dosing changes more than 12 weeks before screening, just the final dose of the medication with inclusive dates should be recorded.

Other than existing allowed concomitant treatment for SLE or LN, other prescription or over-the-counter medications should be administered only if they are prescribed for the treatment of specific clinical events.

[figure not shown]
### **6.10.1 Prohibited and/or Restricted Treatments in Part A and Part B**

Prohibited and/or restricted medications during Part A and Part B are listed below:

1. Administration of opioids unless all the following criteria are met:
  - a. The prescribed dose has been stable for at least 2 weeks before randomization
  - b. In the opinion of the investigator, the subject's use of opioids will not impact the protocol-specific efficacy and safety assessments
  - c. The dose does not exceed the equivalent of 30 mg of morphine per day (see [APPENDIX 15](#) for morphine milligram equivalents of commonly used opioids)
2. Any use of nonsteroidal anti-inflammatory drugs unless approved by the [REDACTED] medical monitor (aspirin is allowed at stable doses no higher than 325 mg/day throughout the study)
3. Lymphocyte apheresis or selective monocyte, granulocyte apheresis (eg, Cellsorba®)
4. Live vaccines during the study or within 2 months after the last dose. Heat-killed (or otherwise inactivated) or protein vaccines such as influenza and pneumococcal vaccines may be received at any time during the study. Any other inactivated vaccines such as tetanus should be used according to local guidelines
5. Immunosuppressants other than MMF, aminoquinolines (eg, hydroxychloroquine), or corticosteroids
6. Use of cyclophosphamide (including ophthalmic), any biologic agent, or other medications listed in [APPENDIX 7](#)
7. Anifrolumab, ustekinumab, or interferon- $\alpha$  kinoid vaccines
8. Exposure to any investigational agent or placebo outside the current study
9. Rescue therapy other than prednisone or equivalent ([APPENDIX 6](#))
10. Modified-release corticosteroid formulations
11. Concomitant medications known to interact with MMF
12. Any other drugs, including over-the-counter medications and herbal preparations except those approved by the [REDACTED] medical monitor

### **6.10.2 Permitted Concomitant Medications in Part A and Part B**

Stable doses of concomitant medication for chronic medical conditions that are not listed in the exclusion criteria ([Section 5.2](#)) or the prohibited and/or restricted treatments ([Section 6.10.1](#)) are permitted in Part A and Part B if approved by the [REDACTED] medical monitor. Dose adjustments of these medications should be avoided during the study unless clinically indicated. If a dose adjustment of these medications should occur, they must be recorded on the Concomitant Medications eCRF or the Diagnostic and Medical Procedures eCRF. The investigator should instruct the subject to notify the study site about any new treatments he or she takes after the start of the study treatment. All medications and significant nondrug therapies (including physical therapy and blood transfusions) administered after the subject starts study treatment must be listed on the Concomitant Medications eCRF or the Diagnostic and Medical Procedures eCRF.

## **7 DISCONTINUATION CRITERIA**

### **7.1 Discontinuation from Study Treatment**

Subjects **MUST** discontinue the IP (and non-IP at the discretion of the investigator) for any of the following reasons:

- A subject requests to stop study treatment; these subjects will remain in the study and must continue to be followed for protocol-specified follow-up procedures, unless the subject specifically withdraws consent for any further contact with him/her or persons previously authorized by the subject to provide this information
- Any clinical AE, laboratory abnormality, or intercurrent illness that, in the opinion of the investigator, indicates that continued participation in the study is not in the best interest of the subject
- Termination of the study or the program by BMS
- Loss of ability to provide consent through imprisonment or involuntary incarceration for treatment of either a psychiatric or physical (eg, infectious disease) illness

In the case of pregnancy, all study treatment must be stopped immediately. The investigator must immediately notify the [REDACTED] medical monitor or designee of this event (no later than 24 hours after becoming aware of the pregnancy). See [Section 8.5.6](#) for more information about pregnancy.

Unless they withdraw consent for further follow-up procedures or lose the ability to consent freely (eg, through imprisonment or involuntary incarceration for treatment of psychiatric or physical illness), subjects who discontinue from the study treatment early should still attend the final

end-of-treatment visit and the 28-day follow-up visit. They will also be followed for SAEs for 30 days after the final dose of IP, and will be evaluated on a case-by-case basis regarding the optional end-of-treatment renal biopsy.

If study treatment is discontinued prior to the subject's completion of the study, the reason for the discontinuation must be documented in the subject's medical records and entered on the appropriate eCRF page.

## **7.2 Week 24 Subject Status Evaluation**

At Week 24 (Visit B7), investigators should assess, based on their clinical judgment, if continuation in the study remains in the subject's best interest, overall and with regard to progression of renal disease. If the investigator determines that continuation is no longer in a subject's best interest, the subject should stop the study treatment immediately, but if possible, should remain in the study for appropriate follow-up procedures as outlined in Sections 7.3 and 7.4. The investigator will record the reason for discontinuation and will report any AEs or SAEs (see [Section 8.5](#) and [APPENDIX 3](#)).

## **7.3 Discontinuation from the Study**

Unless they withdraw consent for further follow-up procedures or lose the ability to freely consent (eg, through imprisonment or involuntary incarceration for treatment of psychiatric or physical illness) subjects who discontinue from the study early should still attend the 28-day follow-up visit. They will also be followed for SAEs for 30 days after the final dose of IP.

Subjects should notify the investigator of the decision to withdraw consent from future follow-up **in writing**, whenever possible.

The withdrawal of consent should be explained in detail in the medical records by the investigator and entered on the appropriate eCRF page.

In the event that vital status (whether the subject is alive or dead) is being measured, publicly available information should be used to determine vital status only as appropriately directed in accordance with local law.

If the subject withdraws consent for disclosure of future information, the Sponsor may retain and continue to use any data collected before such a withdrawal of consent.

## **7.4 Follow-Up After Early Discontinuation from Study Treatment**

In this study, renal response is a key endpoint of the study. Follow-up procedures are of critical importance and are essential to ensuring subject safety and the integrity of the study. Investigators should continue to follow subjects who are discontinued early from the study treatment, for collection of outcome data for 30 days after the final dose of the study treatment, or until death or the conclusion of the study, as required, unless subjects withdraw consent for further follow-up.

## **7.5 Lost to Follow-Up**

Investigative site staff must make reasonable efforts to locate study subjects to determine and report their ongoing status. These efforts include follow-up with persons authorized by the subject to provide information.

A subject will be considered lost to follow-up if there is no response to a minimum of 3 documented phone calls, faxes, or emails, and a registered letter. The site staff will document all attempts at communication in the subject's medical records.

If it is determined that the subject has died, the site will use permissible local methods to obtain date and cause of death.

If the investigator's use of a third-party representative to assist in the follow-up portion of the study has been included in the subject's informed consent, then the investigator may use a Sponsor-retained third-party representative to assist the site staff with obtaining the subject's contact information or other public vital status data necessary to complete the follow-up portion of the study.

The site staff and representatives will consult publicly available sources, such as public health registries and databases, in order to obtain updated contact information.

If after all attempts, the subject remains lost to follow-up, then the last date the subject was known to be alive should be reported and documented in the subject's medical records.

## **8 STUDY ASSESSMENTS AND PROCEDURES**

Study assessments and procedures are summarized in the Schedules of Activities (see [Section 1.3](#)).

Protocol waivers or exemptions are not allowed.

All immediate safety concerns must be discussed with the [REDACTED] medical monitor immediately upon occurrence or awareness to determine if the subject should continue or discontinue treatment.

Adherence to the study design requirements, including those specified in the Schedules of Activities, is essential and required for study conduct.

Procedures not specified in the protocol that are part of standard care may be performed if they do not interfere with study procedures; any data arising from such procedures are not to be reported in the eCRF.

All screening evaluations must be completed and reviewed to confirm that potential subjects meet all eligibility criteria before randomization. The investigator will maintain a screening log to record details of all subjects screened and to confirm eligibility or record reasons for screening failure, as applicable.

### **8.1 Part A Assessments**

Assessments during Part A will be conducted for safety monitoring, [REDACTED] and at Visit A4, evaluation of the criteria to continue in Part B and for randomization.

Women of childbearing potential must have a negative urine pregnancy test within 24 hours of the first dose (or first on-study dose) of MMF, and at each study visit in Part A. Women of childbearing potential who are beginning treatment with MMF in Part A must also have another urine pregnancy test between 8 and 10 days after the first dose of MMF; this test may be performed at a local laboratory, and the site staff will contact the subjects to whom this requirement applies, and remind them to obtain the test either at the investigative site or a local laboratory.

Per the MMF prescribing information, subjects starting MMF in Part A must also have a CBC weekly for the first month, every 2 weeks during the second and third months, and monthly thereafter for the first year of treatment. If the timing of these monitoring CBCs coincides with scheduled study visits, the central laboratory results may be used; if needed in between scheduled study visits, these CBCs may be performed at a local laboratory. Site staff should call subjects to whom this monitoring applies, and remind them to obtain the test either at the investigative site or at a local laboratory.

Most randomization and baseline assessments for Part B will be done at Visit A4, including 24-hour UPCR. Subjects with  $\geq 12$  weeks but  $\leq 24$  weeks of MMF treatment at a dose of 1.5 to 3.0 g/day at the time of screening will attend Visit A4 and will collect a 24-hour urine specimen as soon as eligibility is confirmed. For all other subjects, two 24-hour urine specimens will be collected: one approximately 7 to 10 days before Visit A4, and the other just before Visit A4. See [Section 8.7.3.2](#) for details.

Additional regular laboratory assessments in Part A include the following, not including baseline or randomization assessments only at Visit A4 (See Section 8.2):

- Routine chemistry and hematology
- [REDACTED]
- Trough MPA concentration (at Visit A3; for randomization)
- [REDACTED]
- [REDACTED]
- [REDACTED]
- [REDACTED]
- [REDACTED]
- [REDACTED]
- [REDACTED]
- [REDACTED]
- Urinalysis with microscopic examination (and culture if appropriate)
- UPCR on a first morning voided urine sample (or second sample if the first was not collected)

## 8.2 Part B Assessments

Baseline values may come from assessments at Visit A4 or B1 as indicated in [Table 2](#) and [Table 3](#). All subjects (randomized and nonrandomized) will attend all visits in Part B and will have the assessments listed in [Table 3](#). For premenopausal women, study visits and 24-hour urine collections should be scheduled, when possible, for times when they are not menstruating.

Subjects should be instructed to not take any pain medications for at least 12 hours before their scheduled visits in Part B (except the 28-day follow-up visit [Visit B15]), because these medications may affect some of the assessments.

## 8.4 Efficacy, Safety [REDACTED] Assessments

[figure not shown]
### 8.4.1 Efficacy Assessments

[figure not shown]
The following assessments will be done during the study (see [Section 1.3](#)):

- Laboratory assessments:
  - [REDACTED]
  - Urinalysis with microscopic examination (clean-catch specimen); if the urinalysis is positive for leukocytes, blood, or bacteria, a urine culture should be performed if appropriate
  - UPCr based on the first morning voided urine specimen (if the first morning voided specimen was not collected, the second morning void will be used)
  - UPCr based on 24-hour urine collections:
    - Two 24-hour urine specimens will be collected for Visits A4 (baseline), B7, and B14 (except for subjects with  $\geq 12$  weeks of MMF at a dose of 1.5 to 3.0 g/day at the time of screening, who will collect a single 24-hour urine to be compared to their 24-hour UPCr at screening); if the difference in UPCr values between specimens is  $> 20\%$ , a third 24-hour urine specimen will be collected as soon as possible but no more than 10 days after the results of the results of the first two samples are reported
      - If the third value is within 20% of only one of the previous 2 values, the 2 closest values will be used to compute the average UPCr
      - If the third value is within 20% of both previous values (in the middle), then all 3 values will be used to compute the average UPCr

- If the third value is not within 20% of either of the previous values (all 3 values are > 20% different from each other), then all 3 values will be used to compute the average UPCR
  - [REDACTED]
  - High-sensitivity C-reactive protein (hsCRP)
  - Antiphospholipid antibodies (APAs): anticardiolipin antibody (aCL), lupus anticoagulant (LA), and anti-beta-2 glycoprotein-1 (β2GP1) (immunoglobulin [IgA], IgG, and IgM)
  - [REDACTED]
  - Antinuclear antibody (ANA)
  - [REDACTED]
- Disease activity and damage indices:
  - [REDACTED]
  - SLICC/ACR SDI see [APPENDIX 10](#)
  - rSFI – clinical component only (excluding the renal system, which is assessed with the OSS Flare Index) see [APPENDIX 17](#)
  - OSS Flare Index; see [APPENDIX 16](#)

## 8.5 Adverse Events

The definitions of AEs and SAEs, and contacts for reporting SAEs are in [APPENDIX 3](#).

Adverse events will be reported by the subject or, when appropriate, by a caregiver, surrogate, or the subject's legally authorized representative.

The investigator and any designees are responsible for detecting, documenting, and reporting AEs and SAEs, and remain responsible for submitting follow-up information on SAEs, study treatment-related AEs, and AEs leading to discontinuation of the study treatment or from the study.

Any AEs or SAEs with a start date and time after the first on-study dose of MMF will be considered treatment-emergent with regard to MMF, and any AEs and SAEs with a start date and time after first dose of blinded study treatment will be considered treatment-emergent with regard to blinded study treatment. Investigators will assess whether the events are related to IP.

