  - Approximately 1 week between the last visit in Part A (Visit A4) and the first visit in Part B (Visit B1)
  - Part B: Randomization followed by blinded study treatment for 52 weeks plus continued open-label MMF with or without corticosteroids (or just continued open-label MMF with or without corticosteroids for those who are not randomized); all subjects will attend study visits every 4 weeks and undergo assessments as indicated in [Table 3](#)
  - [REDACTED]
- A follow-up period of  $28 \pm 3$  days followed by an end-of-study visit

After a screening period of up to 28 days, eligible subjects will enter Part A of the study, an open-label MMF run-in period of up to 12 weeks. Subjects may continue taking MMF as previously prescribed (if at a dose of 1.5 to 3.0 g/day) until they reach 12 weeks of treatment or, if not receiving MMF or previously prescribed < 1.5 g/day, subjects will be either started on MMF when they enter Part A or titrated to a dose of 1.5 to 3.0 g/day for the full 12 weeks of Part A. Subjects who have been taking MMF at a dose of 1.5 to 3.0 g/day for  $\geq$  12 but  $\leq$  24 weeks at the time of screening will promptly be evaluated for continuation in Part B and for randomization. The suggested target dose of MMF at the first visit in Part B is 1.5 to 2.0 g/day (maximum 3.0 g/day) unless limited by intolerance or toxicity (refer to [Section 6.1](#) for further details regarding individual target dose).

After at least 12 weeks of open-label MMF treatment of at least 1.5 g/day (either only during Part A of the study or including previously prescribed MMF before and during screening), subjects

will be assessed to determine whether they meet the criteria to continue in Part B (see [Section 4.1.2.1](#)), and whether they meet the randomization criteria (see [Section 4.1.2.2](#)). Those subjects who meet all the criteria to continue in Part B and meet the randomization criteria will be assigned in a double-blind manner (1:1:1) to one of the following treatment groups:

- BMS-986165 3 mg BID + continued open-label MMF with or without corticosteroids
- BMS-986165 6 mg BID + continued open-label MMF with or without corticosteroids
- Placebo BID + continued open-label MMF with or without corticosteroids

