### 8.5.2 Time Period and Frequency for Collecting Information About Adverse Events and Serious Adverse Events

The collection of nonserious AE information will begin at the first dose of MMF in Part A and will continue until the final study visit. The Reference Safety Information in Sections 5.6.1 and 5.6.2 of the IB should be used to determine the expectedness of SAEs for expedited reporting.

All SAEs, including those thought to be associated with protocol-specified procedures must be collected from the time the ICF is signed through 30 days after the final dose of any study treatment. Any SAEs that begin after 30 days after the final dose of study treatment must be reported if assessed as related to the study treatment or any protocol-specified procedure.

Medical occurrences that begin after obtaining informed consent but before the first dose of MMF in Part A will be recorded as medical history on the appropriate section of the eCRF module.

All SAEs will be recorded and reported to the Sponsor or designee within 24 hours after the investigator or designee becomes aware of the event. The investigator will submit any updated SAE data to the Sponsor or designee within 24 hours of learning of the information.

Investigators are not obligated to actively seek AEs or SAEs in former study subjects beyond 30 days after the final dose of any study treatment. However, if the investigator learns of an SAE (including a fatal SAE) after that time and believes the event to be reasonably related to the study treatment or study participation, the investigator must promptly notify the Sponsor.

The method of evaluating and assessing causality of AEs and SAEs and the procedures for completing and reporting/transmitting SAE reports is provided in [APPENDIX 3](#).

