### **8.5.4 Follow-up of Adverse Events and Serious Adverse Events**

Nonserious AEs should be followed until the event resolves, stabilizes, or is reported as an SAE (see [APPENDIX 3](#)).

Follow-up is also required for AEs and SAEs that cause interruption or discontinuation of study treatment and for those present at the end of study treatment, as appropriate.

Nonserious AEs must be recorded and described on the nonserious AE page of the eCRF. Completion of supplemental eCRFs may be requested for AEs such as skin reactions, infections, and/or laboratory abnormalities that are reported/identified during the course of the study.

After the initial AE or SAE report (all subjects), investigators are required to proactively follow each subject at subsequent visits/contacts.

All subjects with SAEs and randomized subjects with AEs will be followed until the event is resolved or resolved with sequelae, until the condition stabilizes or is otherwise explained, or until the subject is determined to be lost to follow-up (as defined in [Section 7.5](#)).

Further information on follow-up procedures is given in [APPENDIX 3](#).

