### **8.5.9 Other Safety Considerations**

Any significant worsening noted during interim or final physical examinations, electrocardiogram, x-ray filming, any other potential safety assessment required or not required by protocol should also be recorded as an AE or SAE, as appropriate, and reported accordingly.

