### APPENDIX 3      **ADVERSE EVENTS AND SERIOUS ADVERSE EVENTS: DEFINITIONS AND PROCEDURES FOR RECORDING, EVALUATING, FOLLOW-UP, AND REPORTING**

#### Adverse Events

Adverse Event Definition:
An adverse event (AE) is defined as any new untoward medical occurrence or worsening of a preexisting medical condition in a clinical investigation participant administered study drug and that does not necessarily have a causal relationship with this treatment.
An AE can therefore be any unfavorable and unintended sign (such as an abnormal laboratory finding), symptom, or disease temporally associated with the use of study drug, whether or not considered related to the study drug.
Events Meeting the AE Definition

• Any abnormal laboratory test results (hematology, clinical chemistry, or urinalysis) or results from other safety assessments (eg, ECG, radiological scans, vital signs measurements), including those that worsen from baseline, considered clinically significant in the medical and scientific judgment of the investigator. Note that abnormal lab tests or other safety assessments should only be reported as AEs if the final diagnosis is not available. Once the final diagnosis is known, the reported term should be updated to be the diagnosis.

• Exacerbation of a chronic or intermittent pre-existing condition including either an increase in frequency and/or intensity of the condition.

• New conditions detected or diagnosed after study intervention administration even though it may have been present before the start of the study.

• Signs, symptoms, or the clinical sequelae of a suspected drug-drug interaction.

• Signs, symptoms, or the clinical sequelae of a suspected overdose of either study intervention or a concomitant medication. Overdose, as a verbatim term (as reported by the investigator), should not be reported as an AE/SAE unless it is an intentional overdose taken with possible suicidal/self-harming intent. Such overdoses should be reported regardless of sequelae and should specify "intentional overdose" as the verbatim term.

Events NOT Meeting the AE Definition

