### Follow-up of AEs and SAEs

If only limited information is initially available, follow-up reports are required. (Note: Follow-up SAE reports must include the same investigator term(s) initially reported.)

If an ongoing SAE changes in its intensity or relationship to study treatment or if new information becomes available, the SAE report must be updated and submitted within 24 hours to BMS (or designee) using the same procedure used for transmitting the initial SAE report.

All SAEs must be followed to resolution or stabilization.

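### The treatment-emergent definition has no worsening clause, so a run-in AE that becomes severe or serious in Part B may be left out of the TEAE summaries, depending on how the site records it

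*Combined protocol and SAP*

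**What the plan says.** Section 8.5 gives the only definition of treatment-emergent in the document. For blinded treatment, "any AEs and SAEs with a start date and time after first dose of blinded study treatment will be considered treatment-emergent". A parallel sentence ties treatment-emergence for MMF to the first on-study MMF dose. Neither mentions an event that starts earlier and then worsens.

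Section 8.5.2 says that collection of nonserious AEs "will begin at the first dose of MMF in Part A and will continue until the final study visit". Section 4.1 describes Part A as "an open-label MMF run-in period of up to 12 weeks".

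Four places bear on how a worsening is handled:

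- Appendix 3 defines an AE as "any new untoward medical occurrence or worsening of a preexisting medical condition in a clinical investigation participant administered study drug", and lists among qualifying events "Exacerbation of a chronic or intermittent pre-existing condition including either an increase in frequency and/or intensity of the condition".
- Section 8.5.9 requires an AE or SAE entry, as appropriate, for "Any significant worsening noted during interim or final physical examinations, electrocardiogram, x-ray filming, any other potential safety assessment required or not required by protocol".
- Section 8.5.4 states: "Nonserious AEs should be followed until the event resolves, stabilizes, or is reported as an SAE".
- Appendix 3, on follow-up, begins "If an ongoing SAE changes in its intensity or relationship to study treatment" and goes on to require that the existing SAE report be updated. Follow-up reports keep the term first reported.

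Section 9.5.1 lists TEAEs, AEs, SAEs, deaths, AEs leading to discontinuation, and AEs by maximum severity and by relationship, summarized by Part B treatment arm.

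**The concern.** Subjects are randomized on top of MMF, with or without corticosteroids, after a period in which AEs are already being recorded. Some AE records can therefore be open at Visit B1. A drug added to existing immunosuppression may show harm partly by making such events worse, and not only by causing new ones. A definition based on onset date alone cannot pick up that kind of harm unless each worsening is entered as a separate event with its own onset, and nothing in the plan requires this.

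Safety and tolerability is a primary objective, and Section 9.6.5 says the Week 24 efficacy and safety results will inform later development. If events are aggravated more often on BMS-986165 than on placebo, more of them would be missing from the active arms' TEAE tables, and the observed difference would shrink.

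**Working it through.** The plan states no figure to reproduce, and the question is one of definition. The check is to follow one kind of event through the text.

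**Inputs.** The onset rule comes from 8.5, the start of AE collection from 8.5.2, the recording rules from 8.5.4, 8.5.9 and Appendix 3, the planned summaries from 9.3.2, 9.5.1 and 9.5.3, and the arm sizes from 9.1 (26 per arm, 52 on BMS-986165 combined).

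**The event.** An AE starts in Part A at mild intensity, is still open at the first blinded dose, and becomes severe or serious later in Part B.

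**Route 1: a new record.** A site relies on Appendix 3, where worsening is itself an AE, or on 8.5.9. It enters the worsening as a separate AE starting in Part B. The onset falls after the first blinded dose, so the event meets 8.5 and is a TEAE.

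**Route 2: one continuing record.** A site follows the update rule for SAEs in Appendix 3, or treats the instruction in 8.5.4 to follow a nonserious AE until it is reported as an SAE as the life of a single event. The original onset in Part A is kept. The event fails 8.5 and is not a TEAE for blinded treatment.

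**Does the text choose between them?**

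- Appendix 3's definition and 8.5.9 say that worsening counts as an AE. They do not say how to date it, or whether an AE already on record gets a second entry.
- Section 8.5.4 does not say which onset date applies when a nonserious AE becomes serious.
- The SAE update rule points to a single record, but only for events that are already SAEs, and it sets no onset rule for the analysis dataset.

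Two sites can therefore both follow the protocol and classify the same event differently.

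**Which events are exposed?** The gap is confined to events already recorded as AEs in Part A and still open at the first blinded dose. Nonserious occurrences between consent and the first Part A MMF dose are medical history (8.5.2), so a later exacerbation is a new AE under Appendix 3. Subjects who enter at Visit A4 have a short window, because about one week is planned between A4 and B1 (4.1).

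**Where else would a Route 2 event show?** The primary safety endpoint (9.3.2) covers AEs from baseline through Week 52 and is not restricted to TEAEs. Section 9.5.1 lists AEs, SAEs and maximum severity alongside TEAEs. It states no rule for AEs that start before the first blinded dose, so whether those tables would include the event is also open. Laboratory worsening would appear in the graded abnormalities, change from baseline and shift tables of 9.5.3.

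**Size.** The documents give no rate of AEs open at Visit B1 and no rate of worsening, so a count of affected subjects cannot be derived. What can be stated is the weight of each subject: 1/26 = 3.8% and 2/26 = 7.7% of a single arm; 1/52 = 1.9% of the combined active group.

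**The case against.** The strongest reply is that the sections work together. Section 8.5 refers the reader to Appendix 3 for what an AE is, and there a worsening is an AE in its own right. On that reading a Part B worsening is an AE that starts in Part B, and the onset rule captures it. This reading is reasonable, and it means exclusion is possible but not certain. It does not close the gap, because the recording rules allow the other reading equally well and no sentence requires a new onset date.

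A reader might infer that the definition drops aggravated infections and neutropenia. The documents do not support these as leading examples. Exclusion criterion 4e bars a known active infection, criterion 3 of Section 4.1.2.1 requires eligibility still to hold, and Table 3 confirms this at B1; a known infection at that point should prevent randomization. Worsening neutropenia would be visible in the laboratory grading and shift tables whatever the AE onset.

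A reader might also infer that the primary safety comparison as a whole is biased. That goes too far. The endpoint is wider than TEAEs, the safety analysis is descriptive with no test specified, and the rule applies to placebo as well. The last point limits the concern but does not remove it: an identical rule loses more events from whichever arm has more aggravation.

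Finally, the text available holds the protocol's statistical section but no separate SAP, so a fuller definition there cannot be ruled out.

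**Conclusion.** The point holds as a gap in definition and recording. Treatment-emergence for blinded treatment rests on onset alone, and the sections on AE follow-up and worsening do not agree on whether a worsened run-in AE gets a new onset. Such an event may be missing from the descriptive TEAE summaries by arm, depending on site practice. If BMS-986165 aggravates existing events, those tables would understate the difference from placebo. This direction is conditional, since nothing in the documents shows that aggravation occurs.

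The conclusion rests on two assumptions: that some AEs are open at the first blinded dose, which the design permits, and that at least some sites keep a single record when an event worsens, which the text permits. The relation between 8.5 and Appendix 3 is an unreconciled gap and not a flat contradiction.

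**What to change.** 1. In Section 8.5 and the SAP, define treatment-emergent for blinded treatment as an AE that starts on or after the first blinded dose, or that starts earlier and increases in severity or becomes serious on or after that dose.
2. Align 8.5.4 and Appendix 3 on one rule for recording the date of a worsening, for example a new record linked to the earlier one, and explain it in an eCRF completion note.
3. Use this definition for the TEAE tables in 9.5.1.

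The cost is one sentence of definition, the aligned recording rule, the eCRF note and slightly more recording work at sites. Appendix 3 already requires intensity to be assessed. Every arm, placebo included, would show a few more TEAEs. Nothing in dosing or patient care changes. The rule is best settled before the Week 24 database lock, because the date of a worsening is hard to reconstruct afterwards.
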